5.2 INCLUSION CRITERIA

Potential subjects are required to meet all of the following criteria for enrollment into the study and subsequent randomization.

1. At least 18 years old.
2. Ankle Brachial Pressure Index (ABI) > 0.75. Calculations will be made using measurements from both posterior tibial and dorsalis pedis arteries as well as both arms AND/OR Skin Perfusion Pressures (SPP) greater than 30 mmHg OR Biphasic PVR OR TBI > 0.60 OR TCPO₂ > 30mmHg.
3. Presence of a VLU extending through the full thickness of the skin but not down to muscle, tendon, or bone. The largest ulcer will be designated the index ulcer and the only one included in the Study. If other ulcerations are present on the same leg the index ulcer must be 2 cm or greater in distance from the wound edge of the other ulcers.
4. Study ulcer (i.e. current episode of ulceration) had been present for at least one month (30 days) prior to the initial screening visit, and is excluded if it has undergone 12 month of continuous high strength compression therapy over its duration.
5. Study ulcer is a minimum of 2.0 cm² and a maximum of 25 cm² at the TV1 Randomization visit.
6. The target ulcer has been treated with documented full compression for at least 14 days prior to randomization.
7. Ulcer has a clean, granulating base with minimal adherent slough at the TV1 Randomization visit.
8. Females of childbearing potential must be willing to use acceptable methods of contraception (birth control pills, barriers, or abstinence). A urine pregnancy test must be administered during screening, and must be negative, for inclusion into the study.
9. Patient understands and is willing to participate in the clinical study and can comply with weekly visits and the follow-up regimen.
10. Patient has read and signed the IRB/IEC approved Informed Consent Form before screening procedures are undertaken.

5.3 EXCLUSION CRITERIA

Potential subjects meeting any of the following criteria will be excluded from enrollment and subsequent randomization:

1. Study ulcer(s) deemed by the Investigator to be caused by a medical condition other than Venous Insufficiency. These may include, but are not limited to: fungal ulcerations, malignant ulcerations, diabetic ulcerations, and ulcerations due to arterial insufficiency.
2. Study ulcer exhibits clinical signs of symptoms of infection at S1 or TV1.
3. Known allergy to the components of the multi-layer compression bandaging, or who cannot tolerate multi-layer compression therapy.
4. Study ulcer, in the opinion of the investigator, is suspicious for cancer should undergo an ulcer biopsy to rule out a carcinoma of the ulcer. The patient may be enrolled after a negative biopsy.
5. Patients with a history of more than two weeks treatment with immunosuppressants (including systemic corticosteroids), cytotoxic chemotherapy, or application of topical steroids to the ulcer surface within one month prior to initial screening, or who receive such medications during the screening period, or who are anticipated to require such medications during the course of the study.
6. Patients on any investigational drug(s) or therapeutic device(s) within 30 days preceding screening (i.e. S1); or patient or physician anticipates use of any of these therapies by the subject during the course of the study.
7. History of radiation at the ulcer site.
8. Presence of one or more medical conditions, as determined by medical history, including renal, hepatic, hematologic, active auto-immune or immune diseases that, in the opinion of the Investigator, would make the subject an inappropriate candidate for this ulcer healing study.
9. Study ulcer has been previously treated with tissue engineered materials (e.g. Apligraf® or Dermagraft®) or other scaffold materials (e.g. Oasis, Matristem) within the last 30 days.
10. Study ulcer requiring negative pressure wound therapy or hyperbaric oxygen during the course of the trial.
11. Ulcers on the dorsum of the foot or with more than 50% of the ulcer below the malleolus are excluded.
12. Ulcers that have healed more than 40% during the screening phase (run-in period) are excluded.
13. Pregnant or breast feeding.

CELLUTOME™ IN VENOUS LEG

14. Known history of having Acquired Immunodeficiency Syndrome (AIDS) or with a history known to be infected with Human Immunodeficiency Virus (HIV).
15. Known uncontrolled Diabetes Mellitus, as measured by an HbA1c > 10%.
16. Patients who are unable to understand the aims and objectives of the trial.
17. Presence of any condition(s) which seriously compromises the subject's ability to complete this study, or has a known history of poor adherence with medical treatment.

6 STUDY SCHEDULE

The study is divided into two phases: Screening and Treatment Phases. The schedules for the protocol-specified assessments and procedures in each phase are detailed below in the following sections. The Schedule of Events tables are presented on the next pages.

6.1 VISIT WINDOWS

Subject visit dates must be scheduled within the visit windows detailed on the Schedule of Events tables. One week equals 7 days.

During the Screening Phase, each visit is scheduled from the S1 visit date, with reference to the allowed visit window.

During the Treatment Phase, each visit is scheduled from the TV1 visit date, with reference to the allowed visit window. For example, the TV2 visit is scheduled for 1 week \pm 2 days after the TV1 visit. TV3 is scheduled for 2 weeks \pm 2 days after the TV1 visit.

SCHEDULE OF EVENTS

Visit	SVs (14 days)	TV1 (rand)	T V	TV3	TV4	TV5	TV6	TV7	TV8	TV9	TV10	TV11	TV12- 13
Weeks from Randomization Date			+1	+2	+3	+4	+5	+6	+7	+8	+9	+10	+11-12
Window Period	0		±2 da	±2 days	±2 days	±2 days	±2 days	±2 day	±2 days	±2 days	±2 days	±2 days	±2 days
Assessment of eligibility	√												
Medical history	√												
Apply Prisma™	√				√				√		√ ^[B]		
Randomization		√											
Ulcer assessments	√		√	√	√	√	√	√	√	√	√	√	√
Physical exam	√												
Vital signs	√												
Pain assessment	√		√	√	√	√	√	√	√	√	√	√	√
Study ulcer photographs	√		√	√	√	√	√	√	√	√	√	√	√
Study ulcer cleaning	√		√	√	√	√	√	√	√	√	√	√	√
Study ulcer debridement	√ ^[A]		√	√	√	√	√	√	√	√	√	√	√
Study ulcer swab	√	√				√				√			
Assessment of compression bandaging	√		√	√	√	√	√	√	√	√	√	√	√
Epidermal graft application		√				√		√ ^[B]		√		√ ^[B]	
Study ulcer dressings and compression therapy	√	√	√	√	√	√	√	√	√	√	√	√	√
Study ulcer closure assessment			√	√	√	√	√	√ ^[C]	√	√	√	√	√
Assess for concomitant medications	√	√	√	√	√	√	√	√	√	√	√	√	√
Assess for AEs and SAEs		√	√	√	√	√	√	√	√	√	√	√	√
Quality of Life, PBI-P and Time-trade off questionnaires		√				√				√			√ ^[D]

[A] – If required per the Investigator’s judgment.

[B] – **Group 2C** subjects only

[C] – Evaluation of wound area reduction since TV1. Subjects in **Group 2A** (SOC), whose study ulcer PAR is < 40%, will become **Group 2C**; the remainder of **Group 2A** subjects will become **Group 2B**

[D]- Questionnaires are to be completed for TV13 only

6.2 SCREENING PHASE

The subject will sign and date the ICF and HIPAA authorization (according to site practices) prior to any study-related procedures. A screening number will be assigned to each subject in successive order of entering the study after signing the ICF at each center, beginning with 001 at each site.

SCREENING VISIT – S1

The following procedures must be performed:

- Informed consent will be obtained prior to any study related procedures and the subject will sign a written Informed Consent Form
- Demographic information will be collected.
- Medical history obtained.
- Concomitant medications assessed.
- Vital signs taken.
- Physical examination performed.
- Pain assessment.
- Ulcer history recorded.
- Study Ulcer Assessments will be recorded.
- Assess signs and symptoms of clinical infection of the study ulcer.
- Vascular assessment.
- Clean the study ulcer using saline.
- Digital photo of the study ulcer.
- Perform swab on study ulcer.
- Debridement of the study ulcer if applicable.
- Application of Prisma™ or allowed antimicrobial dressing (Appendix 19.8).
- Apply multi-layer compression bandaging therapy.
- Assessment of subject's eligibility to continue on in the study.
- Schedule the next visit (S2 or TV1) in one week, if they are still eligible.

6.3 TREATMENT PHASE

TREATMENT VISIT 1 (TV1) – PRIOR TO RANDOMIZATION

The following procedures must be performed:

- Pain assessment

CELLUTOME™ IN VENOUS LEG

- Assess effectiveness of compression bandaging
- Check for any changes in the subject's health and update the Medical History with any changes
- Assess concomitant medications
- Assessment of study ulcer
- Check for signs of clinical infection of the study ulcer.
- Clean the study ulcer with saline.
- Digital photo of the study ulcer
- Debridement, if required to remove non-viable tissue
- If the subject is eligible, perform the following procedures (TV1) immediately.
- If the subject is not eligible, discharge the subject from the study as a screen failure.

TREATMENT VISIT (TV1) – RANDOMIZATION

- Randomize the subject
- Perform swab on study ulcer
- If randomized to the epidermal grafting arm: Harvest epidermal grafts using the CelluTome™ device then apply the grafts to the wound bed. (Procedure detailed in Appendix 10).
- If randomized to standard of care apply provided foam to the ulcer.
- Apply multi-layer compression therapy
- Complete Quality of Life, PBI-P, and Time trade off questionnaires (see Appendices 19.5, 19.6, and 19.2)
- Schedule the next study visit one week later

TREATMENT PHASE VISITS TV2-4, 6, 8, 10, 12

The following procedures must be performed:

- Pain assessment
- Assess compression bandaging
- Assess concomitant medications
- Check for any changes in the subject's health and update the Adverse Events or Serious Adverse Events pages with any events
- Study ulcer closure assessment will be determined by a blinded observer
 - If the study ulcer is 100% re-epithelialized, the subject will be scheduled for a Pre-Healing Confirmation Visit (HCV) one week later
 - If the study ulcer is healed, no other study procedures need to be completed at this visit
- Check for signs of clinical infection. If clinical diagnosis of infection has been made, then the subject can be treated with topical antimicrobials or oral antibiotics, but topical antibiotics CANNOT be used on the study ulcer. During the time that an infection is being treated,

CELLUTOME™ IN VENOUS LEG

treatment with the IP will be stopped.

- Digital photo of the study ulcer
- Apply Prisma™ or approved antimicrobial dressing at TV4, TV8 for both **Groups 1A/2A,2B**; and at TV10 for **Group 2C**.
- Apply provided foam and multi-layer compression bandaging therapy.
- The next visit will be scheduled for one week.

TREATMENT PHASE VISIT TV5 AND TV9

The following procedures must be performed:

- Pain assessment
- Assess compression bandaging
- Assess concomitant medications
- Check for any changes in the subject's health and update the Adverse Events or Serious Adverse Events pages with any events
- Study ulcer closure assessment will be determined by a blinded observer
 - If the study ulcer is 100% re-epithelialized, the subject will be scheduled for a Pre-Healing Confirmation Visit (HCV) one week later
 - If the study ulcer is healed, no other study procedures need to be completed at this visit
- Check for signs of clinical infection. If clinical diagnosis of infection has been made, then the subject can be treated with topical antimicrobials or oral antibiotics, but topical antibiotics CANNOT be used on the study ulcer. During the time that an infection is being treated, treatment with the IP will be stopped.
- Digital photo of the study ulcer
- Perform swab on study ulcer
- If in the epidermal grafting arm: Harvest epidermal grafts using the CelluTome™ device and then apply the grafts to the wound bed. (Procedure detailed in Appendix 10).
- If randomized to standard of care apply the provided foam to the wound.
- Apply multi-layer compression bandaging therapy
- Complete Quality of Life, PBI-P, and Time trade off questionnaires (see Appendices 19.5, 19.6, and 19.2)
- The next visit will be scheduled for one week

TREATMENT PHASE VISIT TV7

The following procedures must be performed:

- Pain assessment
- Assess compression bandaging

CELLUTOME™ IN VENOUS LEG

- Assess concomitant medications
- Check for any changes in the subject's health and update the Adverse Events or Serious Adverse Events pages with any events
- Study ulcer closure assessment will be determined by a blinded observer
 - If the study ulcer is 100% re-epithelialized, the subject will be scheduled for a Pre-Healing Confirmation Visit (HCV) one week later
 - If the study ulcer is healed, no other study procedures need to be completed at this visit
- Check for signs of clinical infection. If clinical diagnosis of infection has been made, then the subject can be treated with topical antimicrobials or oral antibiotics, but topical antibiotics CANNOT be used on the study ulcer. During the time that an infection is being treated, treatment with the IP will be stopped.
- Digital photo of the study ulcer
- Wound will be assessed for percentage area reduction (PAR) since TV1. Subjects in **Group 2A** whose wounds are < 40% will become **Group 2C** subjects and receive a graft at TV 7 and TV 11.
- For **Group 2C** subjects: Harvest epidermal grafts using the CelluTome™ device and then apply the grafts to the wound bed. (Procedure detailed in Appendix 10).
- Apply multi-layer compression bandaging therapy
- The next visit will be scheduled for one week

TREATMENT PHASE VISIT TV11

The following procedures must be performed:

- Pain assessment
- Assess compression bandaging
- Assess concomitant medications
- Check for any changes in the subject's health and update the Adverse Events or Serious Adverse Events pages with any events
- Study ulcer closure assessment will be determined by a blinded observer
 - If the study ulcer is 100% re-epithelialized, the subject will be scheduled for a Pre-Healing Confirmation Visit (HCV) one week later
 - If the study ulcer is healed, no other study procedures need to be completed at this visit
- Check for signs of clinical infection. If clinical diagnosis of infection has been made, then the subject can be treated with topical antimicrobials or oral antibiotics, but topical antibiotics CANNOT be used on the study ulcer. During the time that an infection is being treated, treatment with the IP will be stopped.
- Digital photo of the study ulcer
- **Group 2C** subjects will receive a graft. Harvest epidermal grafts using the CelluTome™ device and then apply the grafts to the wound bed. (Procedure detailed in appendix).
- Apply multi-layer compression bandaging therapy

CELLUTOME™ IN VENOUS LEG

- Complete Quality of Life, PBI-P, and Time trade off questionnaires (see Appendices 19.5, 19.6, and 19.2)
- The next visit will be scheduled for one week

FINAL TREATMENT PHASE VISIT (TV13)

The procedures must be performed:

- Pain assessment
- Assess compression bandaging
- Assess concomitant medications
- Check for any changes in the subject's health and update the Adverse Events or Serious Adverse Events pages with any events
- Study ulcer closure assessment will be determined by a blinded observer
- Clean the study ulcer with saline
- Digital photo of the study ulcer
- Complete Quality of Life, PBI-P, and Time trade off questionnaires (see Appendices 19.5, 19.6, and 19.2)

UNSCHEDULED VISITS

Unscheduled visits may be required in addition to the visits detailed above. Additional visits are at the discretion of the investigator. An example of an unscheduled visit is when a change in compression bandaging is required between scheduled visits. The details of these unscheduled visits with subjects will be recorded in the medical records/source documents and on the CRF.

MISSED VISITS

If a subject misses a visit, the site is to make every effort to have the subject return as soon as possible to make up the visit. Once the subject is seen, he/she is to return to his/her original weekly visit schedule. For example, if a subject was seen regularly on Mondays but missed a scheduled Monday visit and came in on Wednesday, he/she should return the next Monday to maintain his/her weekly Monday visit schedule.

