	
CelluTome™ system at TV1, TV5 and TV9, visits plus SOC (multi-layer compression) (Group 1A) (2) SOC alone (Group 2A).
 
At TV 7, wound assessment will be carried out to evaluate wound healing in Group 2A. Subjects in Group 2A, whose percentage area reduction (PAR) is <40% will be allowed to have CelluTome™ treatment in addition to continuation of SOC and will constitute Group 2C. Group 2C subjects will receive a graft at TV7 and TV11. The remainder of Group 2A subjects will be termed Group 2B subjects. Patient codes will still remain the same to enable tracking continuity.
 
During the Treatment Phase, the wound will be swabbed for protease activity for Group 1A and 2A/B subjects: TV1 (In Group 1A this will be prior to CelluTome™ application), TV5 and TV9 visits.
 
Subjects will be evaluated on a weekly basis during the Treatment Phase. Effectiveness evaluations each week will include Investigator assessment of wound healing and measurements of ulcer size using digital planimetry. At TV4 and TV8, Prisma™ is to be applied to the study ulcer for Group 1A, 2A, and 2B subjects. Group 2C subjects will receive Prisma™ at TV10. Safety evaluations during the Treatment Phase will consist of adverse event assessments at each visit.

Dosage and Frequency of Administration
	
Epidermal grafting will be applied up to three times in Group 1A: TV1, TV5 and TV9. Group 2C subjects will receive up to two grafts: TV7 and TV11.

Duration of Study
	
A run-in period of 2 weeks followed by 12 weeks of active treatment.

Statistical Methods, Power, and Sample Size Calculations
	
Please see the Statistical Analysis Plan in the protocol.

Protease Levels
	
Absolute values of inflammatory proteases (Neutrophil elastase, MMP 8 and 9) will be measured at S1 before application of Prisma™, day 0 before application of Epidermal grafts and week 4 and 8 visits thereafter to determine the effect of protease levels on graft success for Group 1A and 2A/B subjects. The results will be blinded to the Investigators.

Key Words
	
Epidermal Grafts Chronic Wounds Clinical Trial Venous Leg ulcer Protease levels in chronic wounds

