19.2 TIME TRADE OFF EVALUATION

A time-tradeoff (TTO) measurement using an electronic system called Wound-Trade© will be elicited from patients to facilitate the assessment of cost-effectiveness (cost-utility). Value for improving patient quality of life is typically quantified using cost-utility analysis. A cost-utility analysis is defined as a type of cost-effective analysis that compares different procedures and outcomes relative to a person's quality of life. It is the most sophisticated form of economic analysis and typically incorporates utility values. Utility values measure the preference for a health state and range from 0.0 (death) to 1.0 (perfect health). When the change in utility measures conferred by a health care intervention is multiplied by the duration of the benefit, the number of quality-adjusted life-years (QALYs) gained from the intervention is ascertained. This methodology incorporates either the improvement in quality of life and/or length of life, or the value, occurring as a result of the intervention. In wound care, patients' experiences of living with wounds are dominated by symptom management, with all studies showing that the wound and its treatment have a profound effect on quality of life.

WOUND-TRADE©

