19.6 PBI-P – PATIENT BENEFIT INDEX, WOUND VERSION

At the beginning of treatment for each group a patient benefit index questionnaire is given to the patient for completion. It is intended to give the patient a chance to give their goals of treatment:

PBI-P – Patient Benefit Index, wound version

Importance of Treatment Goals

With the help of the following questions, we'd like to know how important the below mentioned goals are to you personally in the **current treatment**.

For each of the following statements, please mark **how important** this treatment goal is to you. If a statement does not apply to you, e.g. because you do not have pain, please mark "*does not apply to me*".

As a result of therapy, how important is it for you to ...		not at all	somewhat	moderately	quite	very	does not apply to me
1	...be free of pain						
2	...have no discharge from the lesion						
3	...not have an unpleasant smell from the lesion						
4	...be healed from the lesion(s)						
5	...be able to sleep better						
6	...feel less depressed						
7	...experience a greater enjoyment of life						
8	...have no fear that the disease will become worse						
9	...be able to lead a normal everyday life						
10	...be more productive in everyday life						
11	...be less of a burden to relatives and friends						
12	...be able to engage in normal leisure activities						
13	...be able to lead a normal working life						
14	...be able to have more contact with other people						
15	...be comfortable showing yourself more						
16	...be less burdened in your partnership						
17	...be less dependent on doctor and clinic visits						
18	...need less time for daily treatment						
19	...have fewer out-of-pocket treatment expenses						
20	...have fewer side effects						
21	...find a clear diagnosis and therapy						
22	...have confidence in the therapy						

Please check once more if you have exactly marked each statement with an 'x'.

Our sincerest thanks for your cooperation!

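### W-QoL, PBI-P and time trade-off are first completed after randomisation at TV1, so these three instruments have no pre-allocation measurement in an open-label trial; pain does

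*Combined protocol and SAP*

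**What the plan says.** Section 6.3 gives two procedure lists for TV1. The first, Prior to Randomization, starts with the pain assessment and ends with the eligibility decision. The second, Randomization, opens with "Randomize the subject". The swab comes next, then the treatment step: "Harvest epidermal grafts using the CelluTome™ device then apply the grafts to the wound bed" in the graft arm, and "If randomized to standard of care apply provided foam to the ulcer" in the control arm. Compression follows, and only then "Complete Quality of Life, PBI-P, and Time trade off questionnaires (see Appendices 19.5, 19.6, and 19.2)". Booking the next visit is the last item.

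The S1 list in Section 6.2 has no questionnaires. In the Schedule of Events (Section 6.1) the row "Quality of Life, PBI-P and Time-trade off questionnaires" has ticks at TV1, TV5, TV9 and TV13, and none under screening.

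On purpose and timing, Appendix 19.6 says "At the beginning of treatment for each group a patient benefit index questionnaire is given to the patient for completion". Appendix 19.2 says the time trade-off "will be elicited from patients to facilitate the assessment of cost-effectiveness (cost-utility)". Appendix 19.4 assigns average utility scores to health states in the simulation model. Cost-effectiveness is a named secondary outcome in the Synopsis and Section 3.

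**The concern.** Patient-reported measures in an open-label trial are best taken first while the subject does not yet know the arm. Here the first answers may already carry an effect of the allocation or of the procedure. The three instruments are exposed to different degrees.

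- **Time trade-off.** It asks about the subject's present condition and has no recall window. In list order, a Group 1A subject answers shortly after suction harvesting at the thigh; a control does not. TV1 is also the one administration at which every randomised subject has an open ulcer (at least 2.0 cm² by inclusion criterion 5), so it bears directly on the utility of the unhealed state.
- **PBI-P.** The first form rates how much the subject wants certain things from the current treatment, including fewer side effects, less treatment time and confidence in the therapy. Such ratings could depend on the arm drawn. The end-of-treatment form refers back to them, and Appendix 19.3 uses PBI-P results to estimate indirect costs.
- **W-QoL.** Its recall period is the last 7 days, which lies almost wholly before allocation. The exposure is smaller, but the answers are still given with the arm known.

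A measurement not taken before allocation cannot be recovered later by analysis.

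**Working it through.** No formula applies and the plan states no figure on this point. The check is a comparison of the procedure lists.

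**Step 1. Count the scheduled administrations before randomisation.**

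| Measure | S1 (6.2) | TV1, Prior to Randomization (6.3) | TV1, Randomization (6.3) | Before allocation |
|---|---|---|---|---|
| W-QoL | no | no | yes | 0 |
| PBI-P | no | no | yes | 0 |
| Time trade-off | no | no | yes | 0 |
| Pain, 0 to 10 | yes | yes | no | 2 |

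The pain cell at TV1 is blank in the Schedule of Events, but Section 6.3 lists pain there and the variable list in Section 9.7 asks for a TV1 pain score.

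**Step 2. How firm is the order?** That the questionnaires follow randomisation is firm: they stand under the Randomization heading, and the preceding list sends eligible subjects straight on to that block. That they follow the graft or foam is an inference from the order of the bullets, which the protocol nowhere calls binding. One item supports reading the list as a sequence. The Synopsis fixes the swab at "TV1 (In Group 1A this will be prior to CelluTome™ application), TV5 and TV9 visits", and Section 6.3 does list the swab before the graft. The Schedule of Events cannot settle the order. It has a single TV1 column, which also ticks concomitant medications, and Section 6.3 places those before randomisation.

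**Step 3. Where are the scores used?** H1 to H8 (Section 9.2) include no test on W-QoL, PBI-P or time trade-off. The Section 9.7 variable list does not name them. H6 uses pain. Time trade-off scores enter through Appendix 19.4: they are matched to the health states recorded in the case report form, averaged by state, and accumulated as weekly utilities. The route to a result is therefore the state averages.

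**Step 4. Compare with the rule for pain.** Section 8.6 has pain scored before dressing changes or other handling of the wound. No reason is given for treating the other instruments differently. At TV5 and TV9 the questionnaires again come below graft or foam, and at TV11 below the Group 2C graft.

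**The case against.** The strongest reply is that little in the plan depends on these first scores. W-QoL and PBI-P are not listed endpoints. The documents never call the TV1 questionnaires a baseline, and no planned analysis takes a change from them or adjusts for them. Appendix 19.6 places the first PBI-P form at the beginning of treatment, which is compatible with giving it once the arm is known. The effects of expectation or disappointment are conjecture. Moving questionnaires at later visits does nothing about allocation, which is known by then.

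Most of this stands, and it limits the point to a minor one. It also rules out three stronger readings that a reader might infer:

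- *That the trial lacks a pre-allocation baseline for patient-reported outcomes in general.* Pain is patient-reported, is the only such measure with its own hypothesis, and is scored twice before randomisation.
- *That a planned change-from-baseline analysis is biased.* None is planned for these instruments.
- *That an arm difference in TV1 utility passes in full into the QALY comparison.* Appendix 19.4 averages utilities by health state; nothing says they are arm-specific or differenced from TV1, and later administrations supply scores too.

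What the reply does not remove is that the first utilities and goal ratings are collected with the arm known, when the same visit already has a pre-randomisation block in which to collect them.

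**Conclusion.** The point holds for three instruments and for every randomised subject (225 planned in Section 9.3). W-QoL, PBI-P and time trade-off have no scheduled measurement before allocation. The primary endpoint, H1 to H8, the sample size and alpha are untouched.

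The consequence is possible reporting bias in the first time trade-off utilities and PBI-P goal ratings, and the absence of a clean baseline should anyone later wish to adjust for one. The documents give no basis for its size, and none is offered here. Its direction is also open: expectation and donor-site discomfort in Group 1A could pull opposite ways.

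The finding of post-randomisation timing rests on the block heading. The further statement that the graft or foam is already in place assumes that sites follow the list in order. This is a free improvement of minor weight.

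**What to change.** 1. In Section 6.3, move the questionnaire line from the TV1 Randomization list to the TV1 Prior to Randomization list, after eligibility is confirmed and before the subject is randomised.
2. Footnote the TV1 tick in the Schedule of Events: completed before randomisation.
3. For consistency with the pain rule in Section 8.6, state that at later visits the questionnaires are completed before wound procedures. Section 6.3 lists them at TV5, TV9, TV11 and TV13, whereas the Schedule of Events has no tick at TV11; reconcile the two in the same edit.

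The cost is a reordered line, a footnote and a sentence. Appendix 19.2 puts the time trade-off interview at a few minutes to 15 minutes, and it is already part of the visit. Placing it after the eligibility decision spares screen failures. Visit count, sample size, power and alpha do not change.
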